14.6 CRIM status

At the Baseline visit, a skin biopsy is obtained for isolation of fibroblasts for assessment of cross reactive immunological material (CRIM) status at the central laboratory. The biopsy should preferably be obtained at least 2 weeks prior to the 1st SOBI003 infusion.

CRIM status values will be listed and summarized.

14.7 ECG

12-lead Electrocardiograms (ECG) are obtained at Screening and at Weeks 1 to 4, 6, 8, 12, and 24. During the treatment period, ECGs are obtained pre-infusion and within an hour after end of infusion, i.e., 4 to 5 hours after start of the infusion.

ECG values will be listed and number and percentage of patients with normal and abnormal results will be summarized by visit and time point.

14.8 Other safety assessments

14.8.1 Echocardiography

At screening and Week 24, an echocardiography is performed to determine if there are any cardiac safety concerns that would prevent the patient from participating in the study.

These measurements will be listed and number and percentage of patients with normal and abnormal results will be summarized.

14.8.2 Physical examination and anthropometry

The physical examination will be performed at Screening, Baseline and at completion of the Week 24 visit.

At Weeks 1 to 4, general appearance and skin at the infusion site are examined prior to start of each infusion, 1 hour (+/- 5 minutes), 2 hours (+/- 5 minutes) and 3 hours (+/- 5 minutes) after start of infusion, within 1 hour after end of infusion, and 6 to 7 and 8 to 12 hours after start of infusion. At Weeks 1 and 2, the examinations are repeated on Days 2, 3, and 5. At Weeks 3 and 4, the examinations are repeated on Days 2 and 3.

At Weeks 5 to 24, general appearance and skin at the infusion site are examined prior to start of each infusion and within 1 hour after end of infusion.

Physical examination data will be listed and number and percentage of patients with normal and abnormal results will be summarized by visit and time point.

Weight is assessed at Screening, Baseline, every 4 weeks during the treatment period in order to determine the actual SOBI003 dose to be administered, and at completion of the Week 24 visit. Weight is hence obtained prior to start of infusion at Weeks 1, 5, 9, 13, 17, and 21. The body weight is obtained either on the day prior to the infusion or the day of infusion, BMI is calculated (see Section 8.4.7).

Height and head circumference are assessed at Baseline, at Week 12 and at completion of the Week 24 visit (if applicable, also at ET of SOBI003 treatment).

Anthropometric measurements will be listed and summarized by visit, including change from baseline.

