7.5.5.7.2 Physical examination and anthropometry

The physical examination performed at Screening, Baseline and at completion of the Week 24 visit will include an assessment of the following: general appearance, skin (including any potential reaction around the infusion site), eyes, ears, nose, neck, lymph nodes, throat, heart, lungs, abdomen, musculo-skeletal system and extremities.

At Weeks 1 to 4, general appearance and skin at the infusion site are examined prior to start of each infusion, 1 hour (+/- 5 minutes), 2 hours (+/- 5 minutes) and 3 hours (+/- 5 minutes) after start of infusion, within 1 hour after end of infusion, and 6 to 7 and 8 to 12 hours after start of infusion. At Weeks 1 and 2, the examinations are repeated on Days 2, 3 and 5. At Weeks 3 and 4, the examinations are repeated on Days 2 and 3.

At Weeks 5 to 24, general appearance and skin at the infusion site are examined prior to start of each infusion and within 1 hour after end of infusion.

Weight is assessed at Screening, Baseline, approximately every 4 weeks during the treatment period in order to determine the actual SOBI003 dose to be administered (Section 7.4.6), and at completion of the Week 24 visit. Weight is hence obtained prior to start of infusion at Weeks 1, 5, 9, 12, 17, and 21. The body weight is obtained either on the day prior to the infusion or the day of infusion.

Height and head circumference are assessed at Baseline, at Week 12 and at completion of the Week 24 visit (if applicable, also at Early Termination of SOBI003 treatment).

Anthropometric measurements should be performed according to standard routines at the study site. Shoes must however be taken off during height and weight assessments.

Height and head circumference are recorded in centimeters and weight in kilograms. For all weight assessments, a scale with at least 100-g accuracy should be used.

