4.2 Selection of study population

4.2.1 Inclusion criteria

A patient must fulfill the following criteria in order to be included in the study:

1. Informed consent obtained from the patient's legally authorized representative(s)
2. Patients with MPS IIIA, as confirmed by both:
 - A documented deficiency in sulfamidase enzyme activity in concordance with a diagnosis of MPS IIIA*, and
 - Normal enzyme activity level of at least one other sulfatase measured in leukocytes
3. Chronological age of ≥ 12 and ≤ 72 months (i.e., 1 to 6 years) at the time of the first SOBI003 infusion and has a developmental age ≥ 12 months at screening as assessed by the VABS-II
4. Medically stable patient who is expected to be able to comply with study procedures

* as determined by the reference ranges applied by the Greenwood Genetic Center

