8.4.3 Baseline and change from baseline

Baseline is defined as the last available assessment prior to 1st infusion of study treatment.

Change from baseline = (post-baseline value – baseline value).

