8.4.7 Body mass index (BMI)

Body mass index (kg/m²) will be derived as weight (kg)/(height(cm)/100)² and rounded to the nearest decimal.

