16.2.8.2 Other Safety Data

Listing 16.2.8.2.1	Vital Signs – Safety Analysis Set
Listing 16.2.8.2.2	Anthropometry (Height, Weight, Body Mass Index and Head Circumference) – Safety Analysis Set
Listing 16.2.8.2.3	Physical Examination – Safety Analysis Set
Listing 16.2.8.2.4	Neurological Examination – Safety Analysis Set
Listing 16.2.8.2.5	12-Lead Electrocardiogram (ECG) – Safety Analysis Set
Listing 16.2.8.2.6	Echocardiography – Safety Analysis Set
Listing 16.2.8.2.7	Immunogenicity in Cerebrospinal Fluid (CSF) – Safety Analysis Set
Listing 16.2.8.2.8	Immunogenicity in Serum – Safety Analysis Set
Listing 16.2.8.2.9	PK Sampling and Concentration Data – PK Analysis Set
Listing 16.2.8.2.10	PK Parameters – PK Analysis Set
Listing 16.2.8.2.11	PD assessments Heparan Sulfate (HS) in Cerebrospinal Fluid (CSF) – Safety Analysis Set
Listing 16.2.8.2.12	PD assessments Heparan Sulfate (HS) in Serum – Safety Analysis Set
Listing 16.2.8.2.13	PD assessments Heparan Sulfate (HS) in Urine – Safety Analysis Set
Listing 16.2.8.2.14	PD assessments Heparan Sulfate (HS) Sampling and Concentration Data – Safety Analysis Set
Listing 16.2.8.2.15	Cross Reactive Immunological Material (CRIM) status at Baseline – Safety Analysis Set

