14.3.4.3 Anthropometry (Height, weight, BMI, and head circumference)

Table 14.3.4.3.1	Anthropometry: Summary by Visit and Change from Baseline – Safety Analysis Set
------------------	--

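### Height, weight, BMI and head circumference in children aged 12 to 72 months are summarised without age- and sex-standardisation, so partial slowing of growth could be masked by expected growth

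*SAP*

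**What the plan says.** The SAP places anthropometry under other safety assessments. On its analysis, SAP 14.8.2 has one sentence: "Anthropometric measurements will be listed and summarized by visit, including change from baseline". SAP 8.4.3 defines change as the post-baseline value minus the baseline value, and SAP 8.4.7 derives BMI as weight over height in metres squared.

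One table is planned, Table 14.3.4.3.1, "Anthropometry: Summary by Visit and Change from Baseline – Safety Analysis Set". One listing is planned, Listing 16.2.8.2.2, "Anthropometry (Height, Weight, Body Mass Index and Head Circumference) – Safety Analysis Set". Safety summaries are by dose cohort (SAP 14), with tables for all patients as well (SAP 7).

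On collection, Protocol 7.5.5.7.2 states: "Height and head circumference are recorded in centimeters and weight in kilograms". SAP 14.8.2 gives the schedule: "Height and head circumference are assessed at Baseline, at Week 12 and at completion of the Week 24 visit". Weight is taken more often because it sets the administered dose.

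The eligible age range in SAP 4.2.1 is "Chronological age of ≥ 12 and ≤ 72 months (i.e., 1 to 6 years) at the time of the first SOBI003 infusion". SAP 4.1 describes an uncontrolled study with 3 patients in each of two cohorts to be analysed.

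**The concern.** Children in this age range are expected to grow over 24 weeks, and by different amounts at different ages. A raw gain in centimetres or kilograms can only be interpreted against what a child of that age and sex should have gained. A concurrent control would supply that comparison and so would a growth reference, but the plan has neither.

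Two things follow:

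- A child who grows more slowly than expected still shows a positive change, so partial slowing does not stand out in the table.
- If one cohort happens to be younger than the other, its raw gain in height will tend to be larger whatever the drug does. Dose and age are then mixed in any comparison of cohorts.

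Elsewhere the SAP does take account of age. Cognition is expressed as a quotient of age-equivalent over chronological age (SAP 13.2.1), and PK and HS results are to be shown by age group where applicable (SAP 15.5.3 and 16.2.3). Anthropometry is collected for safety and gets no such treatment.

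**Working it through.** **Text check.** I looked in both documents for any age- or sex-standardised growth measure: z-score, standard deviation score, percentile, growth chart or reference velocity. There is none for any of the four measures. The plan states no figure for anthropometry, so there is none to reproduce.

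**Illustration, height only.**

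Inputs:
- Treatment period of 24 weeks (SAP 4.1), or 24/52.18 = 0.46 year.
- Normal height velocity *v* of 6 to 12 cm/year across the eligible ages. This is an assumption; the documents give no value.
- Fractional slowing *f*, chosen for illustration.

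Formula: expected raw change = *v* × 24/52.18 × (1 − *f*).

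| Slowing *f* | *v* = 6 cm/year | *v* = 12 cm/year |
|---|---|---|
| none | 2.76 cm | 5.52 cm |
| 25% | 2.07 cm | 4.14 cm |
| 50% | 1.38 cm | 2.76 cm |
| 75% | 0.69 cm | 1.38 cm |
| 100% | 0 cm | 0 cm |

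Lowering the bottom of the range to 5 cm/year gives 2.30 cm without slowing and 1.15 cm at half rate, so the pattern does not depend on the exact choice. Raw change reaches zero only when growth stops.

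**Two cohorts that look alike.** Three children growing normally at 6 cm/year have a mean change of 6 × 0.46 = 2.76 cm. Three children expected to grow at 12 cm/year but growing at half that rate have 12 × 0.5 × 0.46 = 2.76 cm. The mean change is the same in both. This is a limiting case, because it puts one whole cohort at each end of the assumed range.

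**Interval length.** The schedule has one height measurement before treatment, in Weeks −6 to −1 (SAP Table 1), and the last on Day 7 of Week 24. With infusions on schedule, Day 7 of Week 24 is 23 × 7 + 6 = 167 days, or 23.9 weeks, after the first infusion. The change labelled Week 24 therefore spans about 25 to 30 weeks. The 5-week spread alone is worth 6 × 5/52.18 = 0.57 cm to 12 × 5/52.18 = 1.15 cm between children. A z-score taken at the age of each measurement allows for this too.

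**The case against.** The case for leaving the plan alone has real weight.

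- **More than change is reported.** A reader might infer that the SAP shows only change from baseline. It does not: values by visit are summarised and each child's measurements are listed. All of them are unstandardised, however.
- **Some harm would show.** A reader might infer that the table cannot reveal growth harm at all. Weight loss or complete arrest of growth would be visible. The gap is confined to partial slowing.
- **The data set is small and readable.** With 6 patients, and with age and gender listed (SAP 10.1), anyone could plot each child on a growth chart. That is true, but it leaves the choice of reference to the reader after the data are seen.
- **Anthropometry is peripheral.** It is not a named endpoint. Protocol 7.5.5.1.1 counts changes in physical examination findings as adverse events, which gives growth problems another route into the primary endpoint. The nonclinical studies, including the juvenile rat study, reported no adverse effects (Protocol 5.1.3). This limits the importance of the point, but it does not make the table more informative.
- **An age difference between cohorts is not shown.** Younger patients are prioritised (SAP 4.1 and 4.3), and a reader might infer that Cohort 1 is therefore younger. Cohorts open in sequence as patients become eligible, so this need not follow, and no ages are given.
- **The illustration covers height only.** The documents give no basis for the expected direction of normal BMI change, so the claim that slowed growth still gives a positive change cannot be carried over to BMI.
- **A z-score would not isolate a drug effect.** It removes expected growth for age and sex. Without a control or a disease-specific reference, the course of MPS IIIA remains mixed with any effect of treatment.

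**Conclusion.** The point holds in limited form. The planned anthropometry summaries are unstandardised, in an uncontrolled study of children aged 12 to 72 months. Partial slowing of growth could be masked by expected growth, and cohort summaries may be confounded by age if ages differ.

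On the assumed 6 to 12 cm/year, half-rate height growth would still appear as a gain of 1.4 to 2.8 cm, against 2.8 to 5.5 cm expected. These sizes rest wholly on that assumption and apply to height alone. The missing growth reference is a matter of text and needs no assumption.

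The documents do not support the stronger readings that all growth impairment is hidden or that the cohorts are known to differ in age. With six patients, 24 weeks of treatment and no growth endpoint, this is an improvement of low importance.

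**What to change.** In SAP 14.8.2, Table 14.3.4.3.1 and Listing 16.2.8.2.2:

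- Add age- and sex-specific z-scores for height, weight, BMI and head circumference from one named growth reference, fixed before database lock.
- Calculate each z-score at the age on the date of that measurement. SAP 8.4.4 derives age only at first infusion, so this derivation must be added.
- Show each patient's change in z-score beside the raw values. With 3 patients per cohort, the individual changes matter more than the cohort mean.

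The cost is a few lines of SAP text and some programming. Sex, month and year of birth and the measurements are already collected, and no visit or sample is added. SAP 8 describes a combined database with the extension study, so the derivation could be reused there.

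There are three downsides:

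- One reference has to be chosen and defended.
- Setting the day of birth to 15 adds an age error of at most about 16 days, or half a month. The error is the same at every visit for a given child, so it should largely cancel in the change.
- A change in z-score cannot by itself separate drug effect from disease course, and the report should say so.

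This is a change to the analysis only and implies no dose or clinical rule.

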14.8.3 Neurological examination

At Screening and at completion of the Week 24 visit (if applicable, also at Early Termination of SOBI003 treatment), a pediatric neurologist conducts an applicable age-related neurological examination including:

- Cranial Nerves
- Cerebellar function
- Sensory function
- Reflexes
- Motor function

Normal/abnormal status will be captured, and any abnormalities will be specified. Number and percentage of patients with normal and abnormal status will be summarized; all data will be listed.

15 Pharmacokinetic analyses

15.1 Secondary pharmacokinetic endpoint analyses

The PKAS will be used for PK analyses including PK parameter calculations, graphical displays of individual and mean data, and the listings and summarization of PK parameters. Patients with missing PK parameters due to unreliable or missing data will be flagged and excluded from summarization.

The SAF will be used for listing of PK concentrations for all patients who received any amount of IMP. The protocol deviations including the deviations leading to patient's exclusion from PKAS will be shown as flags in the listing.

15.2 Serum PK sampling schedule

Table 7 Detailed PK blood sampling schedule

Week	Time	BW \geq 20 kg No of samples ^a	BW \geq 15 kg No of samples ^a	BW \geq 10 kg No of samples ^a
	Screening	1	1	1
	Baseline	1	1	1
Week 1	4h / End of Infusion	2	2	2 ^c
	6h	2		
	12h	2		
	24h	2	2	
	48h	1		
	72h^b	1	1	
	96h^b	1	1	
	120h	1	1	
Week 1 (2)	168h/Pre-infusion	1	1	1
	4h / End of Infusion	2	2	
Week 3	Pre-infusion	1	1	
	4h / End of Infusion	2	2	
Week 4	Pre-infusion	1	1	1
	4h / End of Infusion	2	2	2
	6h	2	2	
	12h	2	2	
	24h	2	2	2
	48h	1	1	
	72h^b	1	1	1
	96h^b	1	1	1
	120h	1	1	
Week 4 (5)	168h/ Pre-infusion	1	1	1
Week 8	Pre-infusion	1	1	1
	4h / End of Infusion	2	2	2
Week 12	Pre-infusion	1	1	1
	4h / End of Infusion	2	2	2
	6h	2	2	
	12h	2	2	
	24h	2	2	2
	48h	1	1	

Week	Time	BW \geq 20 kg No of samples ^a	BW \geq 15 kg No of samples ^a	BW \geq 10 kg No of samples ^a
	72h^b	1	1	1
	96h^b	1	1	1
	120h	1	1	
	168h	1	1	1
Week 16	Pre-infusion	1	1	1
	4h / End of Infusion	1	1	1
	168h	1	1	1
Week 20	Pre-infusion	1	1	1
	4h / End of Infusion	1	1	1
	168h	1	1	1
Week 24	Pre-infusion	1	1	1
	4h / End of Infusion	2	2	2
	6h	2	2	
	12h	2	2	
	24h	2	2	2
	48h	1	1	
	72h^b	1	1	1
	96h^b	1	1	1
	120h	1	1	
	168h	1	1	1

a If Number = 1; PK blood sample is collected from central venous access port. If Number =2; One PK sample will be collected from the central venous access port and one PK sample will be collected from a peripheral venous line. At the Screening visit 1; from peripheral venous line as no central access port has yet been placed.

b If infusion is prolonged, PK samples will be collected 2h and 8h after End of infusion. Thereafter PK sampling will be conducted according to ordinary PK sampling schedule (refer to CSP Section 7.5.6.1).

15.3 Serum PK endpoints

The following parameters will be derived:

- Serum SOBI003 PK parameters at Weeks 1, 4, 12, and 24 and as applicable at Weeks 16 and 20; $t_{end\ of\ inf}$, $C_{end\ of\ inf}$, C_{max} , t_{max} , $C_{pre-dose}$, C_{trough} , CL , AUC_{0-168h} , $t_{1/2}$

Other parameters may be derived such as accumulation ratios R_{Cmax} , $R_{Ctrough}$, $R_{AUC_{0-168h}}$, fluctuation%, etc.

15.4 CSF PK endpoints

- CSF SOBI003 concentration at Baseline, Weeks 12 and 24

- Ratio of SOBI003 CSF concentration/SOBI003 serum concentration Week 12 and 24: (SOBI003 concentration CSF / SOBI003 concentration serum)*100 (%)

15.5 Presentation of concentration data in serum and CSF

15.5.1 Handling of missing data

Missing concentration data for all patients who are administered scheduled study treatment will be considered as non-informative missing and will not be imputed. No concentration estimates will be provided for missing sample values.

For the derivation of the area under the curve (AUC) and for the individual serum concentration versus time curves, the following rules will apply:

- Concentration values below the assay's lower limit of quantification (LLOQ) in pre-dose samples and in samples taken before the time of the 1st quantifiable concentration will be treated as zero; except for the log-transformed concentrations for graphs, where concentration values below the assay's LLOQ in pre-dose samples will be set to LLOQ/2;
- The sampling time of pre-dose samples relative to dosing will also be treated as zero;
- In case a concentration value pre-dose is not available, the concentration value collected at screening may be used for derivation of AUC;
- Post-dose below LLOQ values after the 1st quantifiable time point will be set to missing;
- Samples taken outside the sampling windows may be excluded from by-time point summary statistics; this will be determined prior to database lock.

For serum concentration summary, the following rules will apply:

- Serum concentrations below LLOQ in pre-dose samples and in samples taken before the time of the 1st quantifiable value will be set to zero;
- The serum concentrations below LLOQ after quantifiable concentration will set to missing.

For CSF concentration summary, the following rules will apply:

- CSF concentrations below LLOQ in the pre-dose samples taken before the time of the 1st quantifiable value will be set to zero;
- The CSF concentrations below LLOQ after quantifiable concentration will be summarized.

No further imputation will be applied to any missing values.

15.5.2 Listing and Presentation of individual PK data

PK concentrations in serum and CSF will be listed for SAF. Flags will be used to show deviations from protocol with the explanation in the footnote.

The actual sampling time of PK blood or CSF sample collection, in relation to start of administration of dose, will be listed for each treatment and will include the deviation in time from the protocol scheduled time, if applicable.

Individual subject serum and CSF concentration data will be listed by subject, time point and SOBI003 dose (mg/kg). Individual subject PK parameters will be listed for the PKAS by subject and will be summarized by treatment group/cohort. Unreliable PK parameters will be listed but flagged and excluded from summary.

The following figures will be produced for individual data for SOBI003:

- Individual serum concentration-time profiles will be presented for each dose level with all patients in the same figure on linear and log-linear scales vs actual time for Weeks 1, 4, 12, and 24. Profiles for patients within the same treatment will be combined.
- Individual trough and end-of-infusion serum concentrations vs dose number for all Weeks combined. Profiles for patients within the same cohort will be combined.
- Scatter plots of CSF concentrations for Weeks 12 and 24 for different treatments.

15.5.3 Summary of serum and CSF PK concentrations

PK results, i.e., SOBI003 concentrations in serum and CSF and PK parameters in serum and CSF, will be presented by dose level using descriptive statistics. In addition, results will be presented by demographic characteristics, e.g., age-group and bodyweight, as applicable.

PK serum and CSF concentration data will be summarized by treatment using the following descriptive statistics: n, number and % LLOQ, arithmetic mean, SD, CV%, minimum, median and maximum.

Mean serum concentrations will not be presented if 1 or more out of 3 patients of the actual values at any one time point in the terminal phase are LLOQ or missing.

Samples taken outside the allowed time windows may be excluded from summarization. This will be determined prior to database lock.

Mean \pm SD serum concentration-time profiles will be presented, combining the curves for all dose levels within the same figure, on linear and log-linear scales vs nominal time.

Mean \pm SD trough and $C_{\text{End of inf}}$ or C_{max} serum concentrations and dose number for all cycles combined. Profiles for cohorts with different dose levels will be combined.

15.5.4 PK parameters derivation

The PK parameters will be estimated as follows:

- The apparent C_{max} and the corresponding T_{max} will be read directly from the concentration-time plot (observed data).
- AUC_{last} is calculated using the log-linear trapezoidal interpolation rule for intravenous model.

Terminal elimination parameters, elimination rate constant and $t_{1/2}$, will be derived as below if sufficient data are available.

The terminal elimination rate constant (λz) will be determined by log linear regression obtained on at least the 3 last quantifiable concentrations and will not include C_{max} ;

$t_{1/2}$ is calculated by the program as $\ln 2/\lambda z$;

The AUC_{0-inf} is calculated by the program as:

$AUC_{0-inf} = AUC_{last} + AUC_{extrap}$ where last is the sampling time point of the last measurable concentration (t_{last}). AUC_{extrap} is calculated by the program as: $C_{last}/\lambda z$, where C_{last} is the observed concentration at time t_{last} and λz is the elimination rate constant during the apparent terminal elimination phase; AUC_{0-inf} will only be presented for patients with a reliable λz ;

For single-dose, CL is calculated by program as (dose/ AUC_{0-inf}) and for multiple-dose, CL is calculated by program as (dose/ AUC_{0-168h});

V is calculated by the program as (dose/ AUC_{0-inf})/ λz ;

Fluctuation % is calculated by the program as $100 \times ((C_{max} - C_{min})/C_{avg})$.

The following PK acceptance criteria will be considered to when the reliability of elimination parameters are assessed:

- Number of points to calculate λz is greater than or equal to 3 excluding C_{max} point;
- Interval for calculation of λz is longer than half-life;
- The adjusted square of the correlation coefficient (Rsquare adjusted) for the goodness of fit of the regression line through the data points must be ≥ 0.75 ;
- $AUC_{extrap} \leq 30\%$.

However, less strict acceptance criteria may be applied, in exceptional cases, since the number of PK samples are limited. PK parameters may be calculated and reported even if the strict criteria are not fulfilled. When PK parameters are based on less strict criteria, this will be described on an individual level.

Accumulation ratios will be calculated as ratio of PK parameters (C_{max} , C_{min} , $C_{End\ of\ inf}$, AUC_{0-168h}) for the last vs 1st dose.

